Overconsumption of foods that result from extensive industrial processing is believed to contribute to the development of obesity. Ultra-processed foods now represent most of the calories consumed in America and their contribution to overall diet has increased in parallel with the rise in the prevalence of obesity over the past several decades. While such correlations are suggestive, the effect of industrial processing per se, independent of dietary macronutrient composition, on *ad libitum* energy intake has not been carefully investigated. Therefore, we will conduct feeding studies in adult men and women to investigate the differences in *ad libitum* energy intake resulting from consuming test diets for a pair of 2-week periods in a randomized, crossover design during a single 4-week period. The test diets presented to participants will be matched for calories, macronutrient composition, sugar, fiber, and sodium, but one diet will be composed of ultra-processed foods whereas the other diet will be unprocessed foods.

1. Introduction and Background

The rise in prevalence of obesity and type 2 diabetes over the past several decades has been mirrored by an increasingly industrialized food system [1] involving substantial refinement of inexpensive “inputs” (primarily corn, soy, and wheat) to generate a seemingly diverse supply of convenient, stable, inexpensive, “added value” foods [2, 3] with supernormal appetitive properties [4, 5]. Ultra-processed foods [6] have becoming increasingly common worldwide [7] and now contribute to the majority of calories consumed in America [8].

Overconsumption of ultra-processed foods has been implicated as a causative factor in weight gain [9] and recommendations to reduce intake of processed foods are shared by a variety of proposed healthy dietary approaches that are widely divergent from a nutrient perspective [10]. Whereas previous studies have examined the effect of single meals varying in their degree of industrial processing on satiety and glycemia [11], no study has yet examined the effect of industrial processing on long-term *ad libitum* energy intake.

2. Study Objectives

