In this study, we will investigate *ad libitum* food intake of 20 healthy adult volunteers who will each complete a 4-week stay at the NIH. During their stay, they will consume an ultra-processed and an unprocessed diet for 2 weeks each, in random order. We will collect information (primary and exploratory endpoints detailed below) about energy intake and metabolic changes, in response to the two test diets. These test diets that will be presented to subjects in amounts exceeding their daily energy requirements; subjects will be instructed to eat as much or as little of each diet as desired.

The diets will be designed using a standard computerized nutrition database, and foods will be selected using a food classification system that categorizes foods as belonging to one of three groups: unprocessed or minimally processed foods, processed culinary or food industry ingredients, or ultra-processed food products [6]. Diets will maximize differences in industrial processing while matching for calories, macronutrient composition, sugar, fiber, and sodium. Each subject will be admitted as an inpatient to the NIH Clinical Center and will stay on the 5SWN Metabolic Care Research Unit (MCRU).

Previous studies have successfully detected significant effects of modifying dietary fat versus carbohydrate on *ad libitum* energy intake over periods of 1-2 weeks [12, 13]. We hypothesize that the degree of industrial processing will also significantly impact *ad libitum* energy intake even if the presented diets are matched for calories, macronutrients, sugar, sodium, and fiber.

Hypothesis: The hypothesis of this study is that an ultra-processed diet will lead to greater mean *ad libitum* energy intake as compared to an unprocessed diet when the meals presented to the subjects are matched for daily calories, macronutrient composition, sugar, fiber, and sodium.

2.1 Primary Aim:

1. To determine differences in *ad libitum* energy intake (kcal) during 2 weeks of eating an ultra-processed diet as compared to 2 weeks of an unprocessed diet matched for presented calories, macronutrient composition, sugar, fiber, and sodium.

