to the unprocessed diet – an effect that was not significantly related to sex or BMI. The increased energy intake was due to excess consumption of dietary carbohydrate and fat, but protein intake was stable between the diets.

The hypothesized mechanisms for the effect of the ultra-processed diet on energy intake include:

- i) The non-beverage energy density of the meals (calories per unit mass) was higher during the ultra-processed versus the unprocessed diet (1.96 kcal/g versus 1.06 kcal/g, respectfully). Therefore, more calories were consumed for a similar mass of food eaten;
- ii) The ultra-processed meals were consumed more rapidly which may have delayed satiety; and
- iii) The protein content of the ultra-processed diet was very slightly lower than the unprocessed diet (14% versus 15.6% of total calories, respectively) which may have led to increased overall energy intake to match absolute protein intake according to the protein leverage hypothesis.

We propose enrolling a second cohort of 20 subjects who will be exposed to a reformulated ultra-processed diet that more closely matches the unprocessed diet regarding non-beverage energy density and protein content. The ultra-processed diet will continue to be matched in terms of daily calories, macronutrient composition, sugar, fiber, and sodium. The ultra-processed diet will be modified to include foods that are typically eaten more slowly. If these factors were the main reasons that original ultra-processed diet led to the observed ~500 kcal/d increase in energy intake over the unprocessed diet, then the reformulated ultra-processed diet should lead to a smaller difference in energy intake between diets. Except for dietary formulation, the study design, procedures, and primary and exploratory aims, will be identical in the 2 cohorts. We will also compare the differences in ad libitum energy intake between ultra-processed and unprocessed diets between cohorts 1 and 2.

3. Study Design

This is a randomized order crossover study of healthy adult volunteers to determine differences in *ad libitum* energy intake when consuming an ultra-processed vs. unprocessed diet matched for presented calories, macronutrient composition, sugar, fiber, and sodium.

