4.18 Reward Prediction Error

A computerized probabilistic procedural learning task, the Probabilistic Selection Task, to assess participants ability to learn from both positive and negative outcomes. Dopamine plays a key role in reinforcement learning. Learning from positive outcomes is thought to be a result of phasic bursts firing of dopamine which stimulates the D1R direct ("Go") pathway and inhibits the D2R indirect pathway ("Stop"). The dip in dopaminergic firing experienced as a result of negative outcomes is thought to support learning to avoid the unrewarded choice. This task trains participants on reward contingencies and then tests their learning strategy to determine whether they are more adept at learning predominantly from positive feedback (suggestive of high phasic dopamine response) or from negative outcomes (suggestive of sufficient degree of dip in phasic and tonic dopamine response). Both phases of the task combined last approximately 25 minutes. Participants may complete this computer based task during the inpatient admission, depending on time.

5. Statistical Analysis

Day to day variability of *ad libitum* energy intake has a standard deviation of about 500-600 kcal/d [35-37]. Therefore, over a 14-day diet period each subject will have a mean energy intake with a standard error of about 130-160 kcal/d and the mean energy intake difference between the study diets will have a standard error of about 190-230 kcal/d. Using the conservative assumption that within-subject energy intake correlations are zero, the 20-subject study cohort will have an 80% power to detect a difference in mean *ad libitum* energy intake between the diets of about 125-150 kcal/d with a Type I error probability of 0.05.

Previous *ad libitum* diet studies comparing mean energy intake between 14 day periods consuming diets differing in macronutrient content have observed differences >250 kcal/d [12, 13] which is greater than the minimum detectable difference for a 10-subject cohort under the same assumptions as above. Therefore, the 20-subject cohort of our study is adequately powered to detect physiologically significant differences in *ad libitum* mean energy intake between the diets.

6. Safety Considerations

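### Does the primary comparison need a written period term and a fixed number of subjects per diet order?

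*Combined protocol and SAP*

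**What the plan says.** The Summary describes test diets eaten "for a pair of 2-week periods in a randomized, crossover design during a single 4-week period". Section 2 says of the participants that "they will consume an ultra-processed and an unprocessed diet for 2 weeks each, in random order", and Section 3 opens with "This is a randomized order crossover study of healthy adult volunteers to determine differences in" intake between the diets. None of these places gives an allocation ratio, block size or number per order. Section 3.3.2 sets the number studied at up to 20. Appendix A shows both orders, with the second diet following directly on the first.

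Section 5 is a power calculation. It takes a day-to-day SD of 500-600 kcal/d, states that "the mean energy intake difference between the study diets will have a standard error of about 190-230 kcal/d", and ends with 80% power at 20 subjects for a difference in mean "energy intake between the diets of about 125-150 kcal/d with a Type I error probability of 0.05". It names no test, model, period term or sequence term. The only analysis method named anywhere is an exploratory analysis of variance of taste by genotype (Section 4.13).

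Section 2.3 reports that cohort 1 found a difference of 508 kcal/d (p=0.0001). For cohort 2 it says that, dietary formulation apart, "the study design, procedures, and primary and exploratory aims, will be identical in the 2 cohorts". If the proposed mechanisms hold, "then the reformulated ultra-processed diet should lead to a smaller difference in energy intake between diets". It adds: "We will also compare the differences in ad libitum energy intake between ultra-processed and unprocessed diets between cohorts 1 and 2". No model is given for that comparison either.

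**The concern.** In a two-period crossover, each subject's diet difference contains the diet effect plus or minus any difference in intake between the two fortnights, with the sign set by the order. If period is left out of the analysis, two things can happen. With equal numbers per order, the period effect cancels from the estimate but stays in the variance, so power falls. With unequal numbers, that trial's estimate also shifts by the period effect times (n1 - n2)/20.

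The plan neither fixes the numbers per order nor says whether period is fitted, and its power figure does not reveal which analysis was meant. At stake would be precision, and the freedom to choose the model once cohort 2 data are seen. Cohort 2 looks the more exposed because a smaller diet difference is expected there if the mechanisms hold, and because its result will be set against cohort 1.

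**Working it through.** **Inputs from the documents.** Day-to-day SD 500-600 kcal/d, 14 days per diet, zero within-subject correlation, 20 subjects, 80% power, alpha 0.05 (Section 5); cohort 1 difference 508 kcal/d, p=0.0001 (Section 2.3). Alpha is taken as two-sided because that reproduces the plan's figure.

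**Assumptions.** Period effects of 50, 100 and 200 kcal/d. The documents give none; at 0 nothing is lost.

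**1. The plan's own figure.**
- SD of a subject's diet difference = SD_day x sqrt(2/14): 500 gives 189.0 and 600 gives 226.8 kcal/d, matching the stated 190-230.
- Standard error of the mean difference = SD/sqrt(20) = 42.26 and 50.71.
- Paired t-test, 19 df: the noncentral t needs 2.954 standard errors for 80% power, so 2.954 x 42.26 = 124.8 and 2.954 x 50.71 = 149.8 kcal/d.
- Period fitted at 10:10, 18 df: 2.963 standard errors, so 125.2 and 150.2 kcal/d.

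Both agree with the stated 125-150. The figure is right and does not discriminate between the two analyses.

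**2. An SD closer to what was observed.** The SD in step 1 counts day-to-day noise only. If cohort 1's p-value came from a two-sided paired t-test with 19 df, t = 4.897, the standard error is 508/4.897 = 103.7, and SD = 103.7 x sqrt(20) = 463.9 kcal/d. The unadjusted detectable difference is then 2.954 x 103.7 = 306.4 kcal/d.

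**3. Power at the detectable difference, 10:10, period omitted** (simulation, 200,000 replicates; 80% with no period effect).

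| Period effect (kcal/d) | SD 189-227 | SD 464 |
|---|---|---|
| 50 | 78-79% | 80% |
| 100 | 71-74% | 79% |
| 200 | 46-56% | 74% |

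The lowest figures pair the largest assumed effect with an SD that leaves out all variation except day-to-day noise. They also apply only at the edge of detectability. At 250 kcal/d, the benchmark in Section 5, power on the plan's SD is still at least 97.6% with a period effect of 200.

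**4. Avoiding double counting at SD 464.** If 463.9 came from an unadjusted test, it already contains any period spread. At 10:10 the residual SD after fitting period is sqrt(463.9^2 - (20/19) x period effect^2) = 461.0, 452.4 and 416.0. With 18 df the detectable difference is 305.4, 299.7 and 275.6 kcal/d, against 306.4 unadjusted. The gain is 1.0, 6.7 and 30.8 kcal/d.

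**5. Unequal orders.** Under simple randomisation (an assumption) the chance of 13:7 or worse is 26%, so 74% of allocations are 12:8 or closer.
- At 12:8 the shift is (12 - 8)/20 = 0.2 of the period effect: 10, 20 and 40 kcal/d. Type I error stays at or below 0.05.
- At 13:7 the shift is 0.3 of it: 15, 30 and 60 kcal/d. Type I error is 5.4-5.5%, 6.3-6.6% and 7.5% on the plan's SD, and 5.1%, 5.4% and 6.2% at SD 464.
- Averaged over unrestricted randomisation, type I error is 0.049-0.051 and mean bias is within 0.3 kcal/d.
- Fitting period has its own price when orders are unequal and there is no period effect: about 2 power points at 12:8 and 4 at 13:7.

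**6. Between-cohort comparison.** Standard error at SD 464 = 463.9 x sqrt(2/20) = 146.7 kcal/d. With opposite splits (8:12 and 12:8) and the same period effect in both cohorts, the shift is 20, 40 and 80 kcal/d, or 0.14, 0.27 and 0.55 standard errors.

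**The case for a change.** The strongest case for a change is that cohort 1's result is known, cohort 2 repeats the design, and whether to adjust for period is an analyst's choice on the primary aim that a sentence could close. Fitting period costs one degree of freedom, about 0.4 kcal/d in detectable difference at 10:10 on the plan's SD, and blocking the order in cohort 2 would remove most of the imbalance.

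Part of this stands. The model and the allocation method are not written down, the gap is not an effect of redaction, and stating them would be tidier. What does not stand is that the omission makes a stated rule or figure wrong. No rule in the plan yields an invalid test, and the power figure holds under both analyses. The material loss depends on a period effect that nothing in the documents suggests, and the largest losses also need an SD well below the one cohort 1 implies. At that SD, with a true difference of 250 kcal/d and a period effect of 50, power is only about 62%; with no period effect it is about 63%. Between-subject variance, not the missing term, is the main limit.

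The adjacent diet periods add nothing to this argument, because a period term does not deal with carryover. Balance at 10 per order could not be assured either, given up to 20 subjects and the withdrawals that Section 8 allows.

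**Conclusion.** The concern does not call for a change. Section 5 omits a detail that an analyst of a two-period crossover would ordinarily supply, and either reasonable choice gives a valid comparison on average over randomisation. The stated 125-150 kcal/d is correct as computed and should not be read as challenged.

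The size rests on assumed period effects. At cohort 1's implied SD, and provided that p-value came from an unadjusted two-sided paired t-test, fitting period at 10:10 gains about 1 kcal/d at a period effect of 50 and 7 kcal/d at 100, on a detectable difference of 306. Only at 200 does the gain reach about 31 kcal/d. Inflation of the type I error needs a realised split of 13:7 or worse together with a period effect; at 13:7 and that SD it is 5.1-6.2%. A period effect near or above 200 kcal/d, if one were shown in the cohort 1 data, would make the choice of model matter more; the documents neither report nor suggest one.

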6.1 Possible Risks and Hazards

Research-related risks in this study include those associated with study procedures, namely blood drawing, indirect calorimetry, respiratory chamber, doubly labeled water, measurement of body composition by dual energy x-ray absorptiometry (DXA), wearing physical activity monitors, continuous glucose monitoring, sleep monitoring, oral glucose tolerance testing, and measurement of liver fat by MRS. There are no study medications, and we do not anticipate any diet intervention-related risks since the study will be under close supervision with trained dietitians/nutrition experts.

Blood drawing. The placement of intravenous needles may cause transient pain, and may also result in bruising, bleeding, and/or clotting at the site of needle insertion. A medical provider will be available should any of these problems occur. There is a possibility that a catheter placement would be unsuccessful or need to be removed. If this should occur, another catheter would be placed. The approximate volume of blood to be drawn for research purposes is as follows:

Research Blood Draws

Screening Visit	Diet 1	Diet 2	Total
10 ml	174 ml	147	331

This is within the NIH guidelines for limits of blood drawn for research purposes (550 ml in any 8-week period).

Oral Glucose Tolerance Test. Subjects may experience faintness, nausea, and vomiting after taking the glucose solution.

Indirect calorimetry. The use of the ventilation hood may cause some minimal discomfort in claustrophobic subjects.

DXA. The amount of radiation during the DXA scan is less than one mrem to the whole body. This radiation exposure is below the guideline of 5000 mrem per year allowed for research subjects by the NIH Radiation Safety Committee. The use of the DXA scan apparatus may cause some minimal discomfort in claustrophobic subjects and may cause some minimal back pain in a small minority of the individuals.

Doubly labeled water. The doubly labeled water procedure has no known risks.

Respiratory chamber. Besides inconveniences that can reasonably be expected as a result of spending an extensive time (24h) in the live-in room calorimeter, there is no risk to subjects' physical health. Claustrophobia is an exclusionary criterion. All subjects will be given an opportunity to experience the metabolic chamber prior to enrollment in the study.

Profile of mood states questionnaire. There is no known risk associated with the POMS questionnaire, however, there is the potential of subjects finding completing the task tedious or some may find the questions probing and too personal in nature to comfortably answer. Subjects will be informed that they do not have to respond to all the questions if they have reservations about sharing such personal information.

DSM-5 Self-Rated Level 1 Cross-Cutting Symptom Measure. There is no known risk associated with this self-report measure. However, there is the potential of discovering clinically relevant information requiring further follow-up. If this is the case, a member of the research team will contact the subject, and appropriate follow up will be planned.

Food frequency questionnaire. There is no known risk associated with the FFQ.

Three-factor eating questionnaire. There is no known risk associated with the TFEQ.

MacArthur Socioeconomic Status (SES) Questionnaire. There are no known risks associated with the MacArthur SES questionnaire although some subjects may find completing the task tedious or some may find the questions probing and too personal in nature to comfortably answer. Subjects will be informed that they do not have to respond to all the questions if they have reservations about sharing such personal information.

Owl and Lark Sleep Questionnaire. There is no known risk associated with the sleep self-assessment.

Hunger and satiety assessment. There are no known risks associated with the hunger and satiety assessment

Sleep Apnea Clinical Score. There is no known risk associated with the Sleep Apnea Clinical Score.

STOP-Bang Questionnaire. There is no known risk associated with the STOP-Bang Questionnaire.

Sensory and palatability assessments. There are no known risks associated with the sensory and palatability assessment.

Physical activity monitors. There are no risks associated with the monitors, but subjects may find them to occasionally be inconvenient.

Continuous Glucose Monitoring System. According to the device manufacturer, there is minimal risk associated with the device. Possible side effects include but are not limited to local infection, inflammation, pain or discomfort, bleeding at the insertion site, bruising, itching. Because this protocol represents the first use of this device by our research team, we do not know the frequency of such complications of the device. A medical provider will be available should any of these problems occur.

Sleep Monitor. Subjects may experience discomfort from the respiratory belt or oximetry probe. A plastic covering of the respiratory belt sensor board safeguards against direct skin contact with electrical parts and wiring. Participants will wear the device over thin clothing.

MRI/MRS. There is a small chance of claustrophobia or muscle-skeletal discomfort from lying partially in the magnet. During the imaging measurement, the noise may be somewhat unpleasant, but ear plugs will be provided for comfort. Although the long-term risk of exposure to a magnetic field is not known, the possibility of any long-term risk is extremely low from the information accumulated over the past ten years.

MRS Warning: Certain implants, devices, or foreign objects implanted in the human body may interfere with the MR procedure. Volunteers who have undergone specific prior surgeries (i.e. heart, brain, gastric bypass, breast augmentation, etc) and/or have implants of specific types may be required to provide their IMPLANT CARD in order to determine implant safety/compatibility with the magnet before a scan is performed. The continuous glucose monitor will be removed prior to the MRS procedure.

Saliva collection for taste genotyping. This is a non-invasive procedure and there are no risks associated with saliva collection. Information regarding genetic results will not be shared with the participants.

Psychophysical taste task: Sucrose and Salt Detection Thresholds. There are no risks associated with assessments of taste detection thresholds.

Psychophysical taste task: Sucrose and Salt Preference. There are no risks associated with assessments of taste preference.

Above-threshold or Suprathreshold sensory function: There are no risks associated with assessments of taste preference.

Slips of Action Paradigm: There are no risks associated with the Slip-of-Action paradigm assessment.

Reward prediction error: There are no risks associated with the Reward Prediction Error assessment.

